Where residents lack capacity to provide consent: According to the Mental Capacity Act, residents will be assumed to have capacity unless it is established that they lack capacity, all practicable steps having been made to help them do so. Many of the residents we will work with have cognitive impairment or dementia, even if there is no formal diagnosis. Where there is a concern that a resident lacks capacity to provide informed consent for themselves to participate in the study, the resident will be assessed for mental capacity by delegated individuals (i.e. the care home staff or the researcher and this will be documented). Where a resident does not have capacity, a 'consultee' will be consulted who will provide assent. If a family member is too frail to be approached, the consultee may be a friend or unpaid carer. The consultee will be provided with information about the study (appendix – consultee PIS_Consent), and they will be asked their advice regarding what the person's views would have been about participating in the research, if they had capacity to make the decision for themselves. They will sign a consultee declaration form (appendix – consultee PIS_Consent).

In the event that a consultee who has an unpaid or non-professional role in caring for the person cannot be identified, or is not willing to act, a nominated consultee will be appointed and consulted prior to including the resident in the study. This may be a member of staff at the care home. They too will sign the consultee declaration form (appendix – consultee PIS_Consent).

Inclusion criteria:

- Resident at the care home and expected to continue to live there for 1 year;
- Currently taking >3 prescribed medicines daily. Vitamin and nutritional supplements and
 moisturising skin preparations will not be counted as 'medicines'. PRN medicines given
 regularly, according to MAR charts, will be included. PRN medicines with no records of
 administration will not be counted.
- Willing and able to give informed, signed consent themselves, or where capacity is lacking, a consultee (as above) who is willing to give advice and assent to the resident participating.

Exclusion criteria

- Not well enough to participate, as screened by their nurses;
- Aged <18;
- Prescribed <4 medicines daily;
- Receiving active palliative care.

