Nurses will receive training including a video as well as comprehensive guidelines. The researcher will visit the care home and provide the training at a time and date convenient to the care home. Community pharmacists and pharmacists who act as a 'back-up' for the study will receive training from the study consultant pharmacist. The research team will remain available for further training and guidance as required throughout the study period.

Using the PADRe Profile with care home residents

Nurse leads in 7 homes will implement the PADRe Profile. They will need to complete the PADRe Profile with each of the residents (up to 26) at least every month, for 3 months as part of normal care. To do this, they will take some observations and ask some questions. All observations and questions are those that are sometimes used as part of normal care and are not invasive. The PADRe Profile checklist will help to determine clinical signs and symptoms of adverse drug reactions. At this time, the nurses will also be asked to complete a record/log/diary of using the PADRe Profile to record how it works during usual care. Both use of the PADRe Profile and recording how it works will take approximately 10 to 25 minutes per resident. We ask nurses that they try to carry out PADRe Profile completion with residents and using existing documentation at least every month or more frequently if medicines are changed. They will then pass it to the prescribers and pharmacists caring for the residents, along with the medication administration records.

Use of the quality of life questionnaire

At the start and end of the study, study nurses will fill in a quality of life questionnaire (the EQ-5D-5L) (Euroqol Group 2009) with the participating residents (EQ-5D-5L English; EQ-5D-5L Welsh https://euroqol.org/eq-5d-instruments/eq-5d-5l-about/). This consists of 5 'tick box' questions and will take approximately 5 minutes. This will determine whether the use of the PADRe Profile has improved (or not) the quality of life of the residents.

Undertaking reviews of the care home residents' nursing and medical notes

Consent for researchers to view patient records will have already been obtained from the residents when they consent to take part in the process evaluation at the start of the study.

The researcher will review these notes using a document review sheet (appendix – review

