notes) before the start of the study and at the end of the study for evidence of use of the new PADRe Profile and any changes in care or outcomes of care.

Introductory and debriefing interviews with care home nurses

Before the implementation of the PADRe Profile, study nurses will be invited to take part in an introductory interview with the researcher who will ask them to discuss their views on medication monitoring and the potential of the PADRe Profile instrument. An interview guide will be used. Their knowledge of medications and adverse drug reactions will not be tested but rather, their views on these as well as their views on the PADRe Profile instrument to be used will be discussed. This interview will take place at the care home and will last approximately 30 minutes. Nurses will also receive a debriefing interview with the researcher at the end of month 2 of the implementation of the PADRe Profile (during its use) and at the end of month 3 of using the PADRe Profile. A separate interview guide will be used for debriefing the study nurses.

Undertaking interviews with the stakeholders

At the end of the study period where the PADRe Profile is used, the researcher will undertake qualitative interviews with stakeholders; 1 GP, 1 Community Pharmacist and 1 Resident Representative from each care home. They will be invited to discuss their experiences of participating in a study where the PADRe Profile is being used. This interview will take approximately 30 minutes and an interview guide will be used.

Study size

We shall introduce medicines' monitoring into 7 care homes, each with 26 residents prescribed >4 medicines (estimated ~90% residents (Jordan et al 2015). In previous work with participants acting as their own controls, de-prescribing occurred in 8.5% more participants (12.1% vs. 3.6%) when ADRe Profiles were used. We hypothesise that the new PADRe Profile will be twice as effective. Based on the reported intra-cluster coefficient (0.02) (Jordan et al 2015), 182 participants will detect this difference with 80% power & 5% significance, allowing for a 5% loss to follow up (Uitenbroek 1997, Killip et al 2004).

Analyses

Both quantitative and qualitative methods of analysis will be used and data will be triangulated.

Statistical analysis

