Differences between before and after the intervention will be calculated for: problems addressed, prescription regimens, NHS use, and compared, adjusting for site (statistician AW). The impact of age, diagnoses, and medicines' use (numbers and types of medicines prescribed8) will be accounted. Resource use, costs, and health economic outcome measures will be described (JR).

Qualitative analysis

Interviews will be analysed by the team using the constant comparative method to identify predictors of successful adoption and any changes to the PADRe Profile, working

arrangements and oversight needed to embed use. This systematic, re-iterative method of comparing and contrasting emerging codes, categories and concepts ensures that theoretical perspectives are embedded in the description of change. Interviews will be coded, categorised, analysed and interpreted by at least two researchers and discussed at team meetings, with guidance and consistency checks.

Diaries/logs will also be analysed in association with interview transcripts.

Ethics

Permission to carry out this study will be given by an NHS Research Ethics Committee.

Following approval, any subsequent amendments will be communicated to the Ethics

Committee as well as the investigators, the study participants, and the trial registry.

Participation in the study is voluntary. All those participating will receive a participant information sheet (PIS) and will need to sign a consent form indicating their understanding of their role in the study. The researcher will also be available to discuss with the participants any questions that they may have.

All participants will be given sufficient time to decide whether they wish to take part. They will be informed that their participation in voluntary and that they are free to withdraw at any time without giving a reason for doing so. Those participants agreeing to be interviewed will be informed that their anonymised data and quotes may be used in any relevant publications.

Care home participants or their representatives will be informed that if they chose to withdraw from the study, their medical care or legal rights will not be affected. They will also be informed that

- sections of their care home health records may be looked at by individuals from Aneurin Bevan University Health Board, Cardiff and Swansea Universities and from regulatory authorities

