1. I confirm that I have read and understood the in (version XX) for the above study. I have had the op ask questions and have had these answered satisfa	portunity to consid		
I understand that my participation is voluntary a time without giving any reason.	ind that I am free to	o withdraw at any	
3.I am happy for the interview to be recorded and information used to inform development of medic	•	e researchers, and the	
4. I agree to the use of anonymised data and quothe the use of a study number assigned to my details.	otes in any relevar	nt publications, and to	
5. I agree to take part in the above study.			
Name of participant (PRINT)	Date	Signature	
Name of person taking consent (PRINT) When completed: 1 for participant: 1 for researcher site file	Date	Signature	

Process questions (review notes) to track use of PADRe.

We shall retrieve information for each PADRe Profile item (attached).

Q1.	How often are PADRe Profiles completed? N in weeks
Q2.	Where stored? Notes / research file / other
Q3.	Note items omitted. LIST
Q4.	Other discrepancies y/n LIST
Q5.	Note which items copied from notes, if possible. LIST
Q6.	Guidelines used y/n
Q7.	Any equipment missing for vital signs? y/n
Q8.	If so, which
Q9.	Profiles juxtaposed with MAR charts? y/n
Q10.	Problems marked LIST n
Q11.	ACTIONS marked LIST n
Q12.	Professionals contacted LIST n
Q13.	Care plan changes LIST n
Q14.	Actions completed LIST n
Q15.	Evidence of pharmacist / prescriber review? y/n
Q16.	Changes in MAR charts LIST n
Q17.	Clinical changes LIST n
Q18.	Any other instruments used to record ADRs? y/n NAME

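### Entry rules keep palliative residents out at recruitment only, so end-of-life withdrawal of medicines could inflate apparent de-prescribing in the uncontrolled 'after' period by an unknown amount

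*Protocol*

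**What the plan says.** Under Recruitment of care home residents, the inclusion criteria ask for a "Resident at the care home and expected to continue to live there for 1 year". The exclusion criteria remove anyone "Not well enough to participate, as screened by their nurses", anyone "Prescribed <4 medicines daily" and anyone "Receiving active palliative care". All are conditions of entry. The text shown has no rule for separately classifying a resident who becomes palliative or dies after entry. The nearest provisions are voluntary withdrawal (Ethics) and a 5% allowance for loss to follow-up (Study size).

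The profile is used "at least every month, for 3 months as part of normal care". Notes are reviewed before the start and at the end of the study.

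The Study size section rests on earlier work in which "de-prescribing occurred in 8.5% more participants (12.1% vs. 3.6%) when ADRe Profiles were used", with participants as their own controls, and assumes the new profile is twice as effective. The Statistical analysis section states: "Differences between before and after the intervention will be calculated for: problems addressed, prescription regimens, NHS use". The comparison adjusts for site and accounts for age, diagnoses and medicines' use. There is no concurrent control group.

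On the notes review sheet (process questions), item Q16 reads "Changes in MAR charts LIST n". It has no required field for the date of a change or the reason for it.

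**The concern.** A before-after comparison in the same residents is fair only if background causes of the outcome can act equally in both periods. Here one of them cannot. A resident whose medicines were already being withdrawn at the end of life would have been in palliative care or judged unwell, and so not recruited. The four-medicine floor pushes the same way, because a resident whose list had already been cut below four cannot enter. After entry, nothing prevents either event.

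Some medicines could therefore be stopped in the after period because residents declined, and be credited to the profile. The error would favour the intervention and present a marker of decline as a benefit. The planned adjustment for age, diagnoses and medicines' use does not name palliative status. The base rate is low (0.036 × 182 ≈ 7 residents), so a few such cases would matter.

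**Working it through.** **The plan's own figure.** Inputs from Study size: 3.6% base, 8.5-point earlier difference, doubled to 17 points (20.6%), 7 × 26 = 182 residents, intra-cluster coefficient 0.02, 80% power, 5% significance, 5% loss.

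- Two independent proportions, 3.6% v 20.6%, two-sided, pooled variance, no continuity correction: 57 per group.
- Design effect: 1 + (26 − 1) × 0.02 = 1.5.
- Total: 57 × 2 × 1.5 / 0.95 = 180, against 182 stated.

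The stated size is thus reproduced closely on the de-prescribing outcome, and it is not in dispute here.

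**Illustrative bias.** Let p₀ = 0.036 be the de-prescribing rate in both periods if the profile does nothing. Let q be the share of residents who become palliative during the three months. The documents do not give q, so the values below are assumptions. If every such resident is counted as de-prescribed and the others keep the base rate:

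after rate = p₀(1 − q) + q, so the spurious difference = q(1 − p₀) = 0.964q.

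| q (assumed) | Residents of 182 | Spurious difference | Share of 8.5 points | Share of 17 points |
|---|---|---|---|---|
| 2% | about 4 | 1.9 points | 23% | 11% |
| 5% | about 9 | 4.8 points | 57% | 28% |
| 10% | about 18 | 9.6 points | 113% | 57% |

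**Effect on the error rate.** Because the same residents supply both periods, the effective number per period is taken as 182 × 0.95 / 1.5 ≈ 115. Treating the periods as independent samples, the chance of a significant result with no true effect is about 10%, 34% and 75% in the three rows, against a nominal 5%. This is a rough approximation, since the real comparison is paired.

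**If some are lost before the closing review.** Let r be the share of these residents who still contribute an after record, with those lost dropped from both periods. The spurious difference becomes q·r(1 − p₀) / [1 − q(1 − r)]. For q = 5% and r = 0.5 this is 0.05 × 0.5 × 0.964 / 0.975 = 0.025, or 2.5 points instead of 4.8. At r = 0 it is zero. The table is therefore the upper end for each q.

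**The case against.** Applying eligibility at entry only is normal practice, and removing residents afterwards would itself condition on a post-baseline event. The definition of a de-prescribing event and the handling of death or palliative transition are often left to a statistical analysis plan, which is not shown. Residents screened as well and expected to stay a year should rarely become palliative within three months, and some who do will have no closing review. Each of these points stands in part. They limit the size, but they do not remove the asymmetry, which comes from three things this protocol fixes: entry-only rules, no concurrent control, and a review sheet that does not require date or reason. An analysis plan cannot reliably separate end-of-life changes if those facts are not collected. The closing review uses notes, with access agreed at the outset, so deterioration or death need not remove a resident from it.

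Some stronger readings are tempting but unsupported:

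- A reader might infer that item Q16 cannot show the direction of a change, or that it counts vitamins, emollients and finished short courses as de-prescribing. The item asks for a list as well as a number, so drug and direction can be written down. Nothing says that its count is the endpoint, neighbouring items record care plan and clinical changes, and the attached profile items are not shown.
- A reader might infer that the criteria select on the outcome. They select mainly on health status. Only the four-medicine floor touches prescribing directly.
- A reader might infer that de-prescribing is bound to rise even without an effect. The documents say nothing about prescribing at the end of life, and the before window has no stated length. A rise is possible, not certain.

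**Conclusion.** The point holds as a one-directional risk of bias of unknown size. As planned, withdrawal of medicines at the end of life can enter the comparison essentially only after recruitment, and nothing requires the data that would identify it. 'Essentially' is needed because the before window is undefined and a resident could become palliative between consent and first use of the profile.

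The figures of 1.9, 4.8 and 9.6 points rest on assumed transition rates of 2%, 5% and 10%, on every such resident being counted as de-prescribed, and on all of them reaching the closing review. A reader might infer from them that this mechanism explains most of the earlier 8.5-point effect. The documents do not support that: they give no transition rate, the calculation takes the maximum bias at each rate, and even 10% reaches only 57% of the 17 points used for sizing. What they support is that the contribution could matter and would go unseen. This calls for an inexpensive improvement and does not invalidate the design.

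**What to change.** Keep all residents in the study and leave the eligibility rules as they are.

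1. On the notes review sheet, item Q16, record for each listed change its type (stopped, reduced, started, increased, short course ended), its date and the reason given in the notes. Add one field for the date any palliative care began.
2. In the Statistical analysis section, state that the prescription-regimens comparison will report de-prescribing for all changes and, as a named sensitivity analysis, excluding changes made for palliative care or after it started. Tabulate the excluded changes separately.

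Cutting off the main count at the start of palliative care is not proposed. It would shorten follow-up in the after period alone and could discard genuine profile-prompted changes.

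The cost is extra abstraction for up to 182 residents from notes already being reviewed, and a sentence or two of analysis text. The after-period de-prescribing rate may look less favourable in the sensitivity analysis.

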a) be inclusive of all commonly prescribed medicines to older adults; and, b) tested in a diverse range of care home contexts, including in new socio-economically deprived geographical area away from the current research centre.

Objectives

This new funding will test whether the intervention can identify adverse events in those without mental illness and prevent pain, nausea, vision and dental problems in care homes without academic research support, in an area of greater socio-economic deprivation.

This project aims to:

- Record how the PADRe Profile works during usual care.
- Record any changes to care or prescriptions.

• Record any benefits and harms to residents.

• Estimate changes in quality of life and costs emanating from the intervention.

• Make recommendations as to how the PADRe Profile can be sustained during usual care.

The ADRe Profile improved care and prevented serious adverse events in care homes and

adult mental health teams in Abertawe Bro Morgannwg and Hywel dda UHBs, with the

support of the author (SJ) and her students (Jordan et al 2015, Jones et al 2016). We are

now extending the work to consider all medicines commonly prescribed in primary care:

amongst older adults receiving nursing home care, the prevalence of potentially

inappropriate prescribing is estimated to be 18.5%-82.6% (Dreischulte et al 2016).

Secondary research questions/objectives:

To document the extent to which the PADRe Profile fulfills its aims to:

• minimize adverse drug reactions without compromising the beneficial effects of medicines

• identify, monitor and ameliorate any possible adverse drug reactions associated with

medicines commonly prescribed in primary care

• ensure problems are communicated to pharmacists and prescribers efficiently

• provide practical detail for implementation

• facilitate shared decision-making with residents and within the multi-disciplinary team

Methods

6

Study Design

We will undertake an observational study. This will involve the following:

• an analysis of polypharmacy-related reports in the National Reporting and Learning

System (NRLS),

• a cognitive interview study with volunteers to review the PADRe Profile

• an eDelphi Study with experts to assess the modified PADRe Profile and

• a process evaluation (appendix – study flow diagram) to evaluate the practical use of

the PADRe Profile with 182 care home residents within 7 care homes in the ABUHB

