Recruitment of nurses to administer the PADRe Profile: Care home nurses (with or without NMC registration) will be invited to take part in the study by the Matron/Care Home Manager. One study lead nurse and one deputy lead nurse will be required and both will need to read a participant information sheet and sign a consent form with the researcher (appendix - Health professionals PIS and consent).

Inclusion criteria

- Working in care home, and expected to continue in employment for at least 6 months
- Qualified to administer medicines in the care home, trained in medicines' administration (DH 2016), either through NMC registration or appropriate qualifications, including QCF (Qualifications and Credit Framework 2012) and
- Willing and able to administer the PADRe Profile monthly

Exclusion criteria

- Not trained in medicines' administration
- Not undertaking medicines' administration
- Unwilling or unable to administer medication monitoring

Recruitment of community pharmacists; The researcher will initially ask the care home for the names and contact details of the pharmacists who are aligned to them. Community pharmacists will then be invited to take part in the study by the study Consultant Pharmacists (TB, JH) using a PIS and consent form (appendix – Health Professionals PIS and consent) by letter and email. Pharmacists will be required to sign a consent form.

Inclusion criteria:

- Aligned to a study care home and expected to continue employed as a pharmacist for a t least 6 months
- Willing and able to administer the PADRe Profile monthly

Recruitment of stakeholders for interviews: Study stakeholders (1 GP, 1 pharmacist and 1 consultee per care home) will be invited to carry out an interview by the researcher (appendix – Health professionals PIS and consent; appendix – consultee PIS and consent), verbally or by way of an email. All stakeholders who undertake an interview will be required to sign a consent form with the researcher undertaking the interview.

Inclusion criteria

- GP aligned to a participating nursing home and caring for the recruited participants
- A Community pharmacist aligned to a participating nursing home
- A person who is representing a resident who is participating in the study

Exclusion criteria

- Not involved with residents in care homes
- Unwilling to consent to audio recorded interview

Training the care home nurses and community pharmacists

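### The Protocol says one EQ-5D-5L before and one after will determine whether PADRe improved quality of life, but with no comparator and forms completed by the nurses who deliver PADRe, they can only describe change

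*Protocol*

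**What the plan says.** Under the heading Use of the quality of life questionnaire, the Protocol sets the timing and the assessor: "At the start and end of the study, study nurses will fill in a quality of life questionnaire (the EQ-5D-5L"). The nurses do this together with the residents who take part. The purpose is then given: "This will determine whether the use of the PADRe Profile has improved (or not) the quality of life of the residents".

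Protocol, Objectives, lists as an aim: "Estimate changes in quality of life and costs emanating from the intervention".

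The design is set out elsewhere in the Protocol:

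- Study Design: "We will undertake an observational study".
- Using the PADRe Profile with care home residents: "Nurse leads in 7 homes will implement the PADRe Profile", at least monthly for 3 months. These are all the homes in the process evaluation. No control homes, control residents or control period are described.
- Recruitment of nurses to administer the PADRe Profile: "One study lead nurse and one deputy lead nurse will be required". The sections that follow use the term study nurses for those who are interviewed before PADRe starts and debriefed on using it.
- Statistical analysis: before-after differences are to be calculated and compared, adjusting for site, for problems addressed, prescription regimens and NHS use. Age, diagnoses and medicines are to be accounted for. Quality of life is not in that list. Resource use, costs and health economic outcome measures are only to be described.

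**The concern.** To determine whether PADRe improved quality of life is a causal task, and the words in brackets make the claim run both ways: a rise would show that PADRe worked, and no rise that it did not. The objective makes the same attribution for quality of life and for costs. Both need some way of knowing what EQ-5D-5L would have done over the same months without PADRe, and the design supplies none.

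The reading of the results is at stake. A favourable drift could be reported as benefit, and ordinary decline in a frail population could be reported as PADRe failing. The Dissemination section sends results to the inspectorate and to government, with policy-level introduction as the ultimate goal, so the wording of the claim will carry weight with readers outside the study.

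**Working it through.** **Inputs, all from the Protocol.** 7 homes of 26 residents; 5% loss to follow-up; intra-cluster coefficient 0.02 (Study size). Two EQ-5D-5L forms per resident, completed with the study nurses (Use of the quality of life questionnaire). Adjustment for site, age, diagnoses and medicines (Statistical analysis).

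**1. The plan's own figure.** 7 × 26 = 182. The power statement concerns de-prescribing. Reading 'twice as effective' as a doubled difference, 2 × 8.5 = 17 points, the rates are 3.6% and 3.6 + 17 = 20.6%. A two-sided 5% test with 80% power needs 57 per group. The design effect is 1 + (26 − 1) × 0.02 = 1.5. The total is 2 × 57 × 1.5 / 0.95 = 180, close to 182. So the figure can be reproduced, but as a two-group calculation for another outcome. It provides neither a comparator nor a power statement for EQ-5D-5L.

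**2. Exposure.** Homes exposed: 7 of 7. Residents exposed: 182 of 182. Controls: 0. Expected before-after pairs: 182 × 0.95 = 172.9, about 173.

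**3. What the mean change contains.** Let D be the mean of end score minus start score. Then

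E(D) = effect of PADRe + time trend + effect of who is lost + change in how the nurse-completed form is filled in.

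The two forms yield one mean change, and the right-hand side has four unknown terms. Every resident is unexposed at the first form and exposed at the second, so exposure and period coincide exactly. With a single form before PADRe, no prior trend can be estimated and carried forward.

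**4. Sample size.** More residents shrink the standard error of D. With twice the homes and the same cluster size it falls by a factor of √2. The last three terms in step 3 do not change. A larger study would estimate the same mixture more precisely.

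**5. Adjustment.** Site is constant across the two forms. Age, diagnoses and medicines may explain why some residents change more than others. None of them provides unexposed follow-up, so none separates PADRe from period, attrition or assessor expectation. No later analysis of these two forms alone could do so, and the problem is therefore not a detail that an SAP can settle.

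**6. Who completes the form.** The nurses recruited to administer PADRe, those interviewed and debriefed about it, and those who fill in EQ-5D-5L are all called study nurses. That they are the same people is an inference from this usage; no single sentence says so. On that reading they know of PADRe use and are not blind. Without it, steps 2 to 5 still stand on the missing comparator and the two time points.

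**7. The sections side by side.** The questionnaire section says determine, the Objectives attribute change to the intervention, and the Statistical analysis section says describe. The Data confidentiality section handles EQ-5D-5L together with resource use and health economics, which places it under the descriptive plan. The descriptive wording is the one that fits the design.

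**The case against.** The strongest reply is that the working plan is already modest. The title presents a quality improvement process intervention, the design is called observational, EQ-5D-5L is absent from the before-after comparisons, and health economic measures are to be described. On this view one loose sentence is at odds with a sound section. That stands as a limit on the weight of the point: this is a wording correction, and notes review and triangulation remain useful for interpreting any change. It does not remove the point, because the sentence tells readers what the result will mean.

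Four stronger readings are tempting, and the documents do not support them.

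- *That a false-positive rate can be attached.* One could assume a drift in EQ-5D-5L and compute how often an interval would exclude zero. The Protocol states no test or interval for EQ-5D-5L, any drift would be invented, and the intra-cluster coefficient was not reported for this outcome. If scores truly move, an interval excluding zero is also right about change; the error arises only when the change is attributed to PADRe.
- *That cognitive impairment makes the form largely the nurse's opinion.* The Protocol says "Many of the residents we will work with have cognitive impairment or dementia, even if there is no formal diagnosis", but it also says the form is completed with residents. How impaired residents answer is procedural detail that may sit elsewhere.
- *That the introductory interview primes the nurses.* It asks them to "discuss their views on medication monitoring and the potential of the PADRe Profile instrument". This seeks views and does not promote a favourable one, and its order relative to the first EQ-5D-5L is not stated.
- *That no cost can be attributed.* The cost of delivering PADRe, at about 10 to 25 minutes per resident, arises from the intervention by definition and needs no control group.

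**Conclusion.** The concern holds, limited to what EQ-5D-5L can show by itself. The Protocol promises a causal answer from an uncontrolled before-after comparison on two forms completed by unblinded study nurses. A change in either direction can be estimated but not attributed to PADRe, and this is so at any sample size. The same limit applies to the objective's wording on quality of life and on overall costs, but not to delivery cost.

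In scope, it covers the whole cohort: 7 of 7 homes and 182 of 182 residents, with no comparator. In magnitude, no bias can be computed from the document.

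The conclusion rests on two readings: that no concurrent or staggered comparator exists because none is described, and that the study nurses who complete the form are those who deliver PADRe. Only the assessor part depends on the second. A reader might infer that the study needs a control group or that its sample size is wrong. Neither follows: a descriptive process evaluation can proceed as designed, and the 182 was set for de-prescribing.

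**What to change.** Three changes of wording in the Protocol:

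1. Use of the quality of life questionnaire: replace the sentence on determining improvement with *EQ-5D-5L will describe change in residents' quality of life over the study period.*
2. Objectives: replace the quality-of-life and cost aim with *Estimate changes in quality of life and in NHS resource use and costs over the study period, and the cost of delivering the intervention.* This keeps the one cost that can be attributed without a comparator.
3. Add: *Because there is no concurrent control and the form is completed with the nurses who deliver PADRe, a change in EQ-5D-5L in either direction cannot by itself be attributed to PADRe.*

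The changes bring these sections into line with the Statistical analysis section. They need no new data, visits, staff or residents. The cost is giving up an attributed quality-of-life claim, and an attributed change in overall costs, that the design cannot support.
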